#### Abbreviation

Term	Definition		
ADR	Adverse Drug Reaction		
AE	Adverse Events		
ALT	Alanine Transaminase (SGTP)		
AST	Aspartate Transaminase (SGOP)		
ATC code	Anatomical Therapeutic Chemical code		
ВМІ	Body Mass Index		
CMAP	Compound Muscle Action Potential		
CMT	Charcot-Marie-Tooth disease		
CMT1A	Charcot-Marie-Tooth disease subtype 1A		
CMTNS-v2	Charcot-Marie-Tooth Neuropathy Score Version 2		
FAS	Full Analysis Set		
НСТ	Hematocrit		
HGF	Hepatocyte Growth Factor		
ICH	International Conference on Harmonization		
IND	Investigational New Drug		
IΠ	Intent-to-Treat		
KGCP	Korea Good Clinical Practice		
MCH	Mean Corpuscular Hemoglobin		
MCHC	Mean Corpuscular Hemoglobin Concentration		
MCV	Mean Corpuscular Volume		
MedDRA	Medical Dictionary for Regulatory Activities		
MPV	Mean Platelet Volume		
MRI	Magnetic Resonance Imaging		
NCV	Nerve Conduction Velocity		
NCAM	Neural cell adhesion molecule 1		
ONLS	Overall Neuropathy Limitation Scale		
PPS	Per-Protocol Set		
PT	Preferred Term		
PV	Pharmacovigilance		
p75	p75 Neurotrophin receptor		
RBC	Red Blood Cell		
SAE	Serious Adverse Event		
SAP	Statistical Analysis Plan		

**SNAP** 

Sensory Nerve Action Potential

Term	Definition	
SOC	System Organ Class	
SOP	Standard Operating Procedure	
TEAE	Treatment-Emergent Adverse Event	
10MWT	10-meter walk test	
WBC	White Blood Cell	
WHOART	WHO Adverse Reactions Terminology	

### 1. Objective and Background of Clinical Study

Single Center, Open label, Repeat Intramuscular Administration, 270days, Phase I/2a Clinical Trial to Evaluate Safety and Tolerability of Investigational Product (Engensis: VM202) in Patients with Charcot-Marie-Tooth Disease Subtype 1A (CMT1A)

#### 1.1 Objective of Clinical Study

To assess the safety and tolerability of the investigational product (VM202) injected in the weakened lower limb muscles of CMT1A patients.

### 1.1.1 Primary Objective

To evaluate safety and tolerability following repeated doses of the investigational product (VM202).

#### 1.1.2 Secondary Objectives

To evaluate efficacy following repeated doses of the investigational product (VM202).

- (1) Changes in severity of disease
  - CMTNS-v2 (Charcot-Marie-Tooth Neuropathy Score version 2)
  - FDS (functional disability scale)
- (2) Changes in lower limb function
  - ONLS (overall neuropathy limitation score) leg scale
  - 10MWT (10-meter walk test)
- (3) Changes in fatty infiltration level of lower limb muscles
  - MRI leg
- (4) Nerve regeneration potential
  - CMAP (compound motor nerve action potential)
  - SNAP (compound sensory nerve action potential)
  - NCV (nerve conduction velocity)
- (5) HGF antibody generation by VM202

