3.6 Engensis; VM202

Hepatocyte growth factor is known to bind to the c-Met receptor on the cell membrane having tyrosine kinase activity and promoting various cell division, migration, and angiogenesis, as well as inhibiting apoptosis.[55]

Two difficulties must be overcome to deliver a target quantity of exogenous HGF. The first difficulty is that HGF is unstable in the bloodstream, and the second is that it is rapidly metabolized in the liver; the in vivo half-life of HGF is 15 minutes.[56][57]

Thus, a way to increase the available HGF in neurons is to develop a gene delivery strategy that allows continuous expression of HGF protein in vivo. Although plasmid DNA has the lowest efficiency among the gene transfer systems that have recently used, using local targeted delivery is a highly attractive choice (especially in skeletal muscles) due to the facts that its persistence in vivo is limited and that gene insertion is unnecessary.

Engensis (VM202) is the drug developed to achieve this very objective, and it is the study drug that will be used in this clinical study. Engensis (VM202) is a DNA plasmid containing a new recombinant HGF gene (HGF-X7) that has been made to simultaneously express two isoforms (HGF₇₂₃, HGF₇₂₈) of the hepatocyte growth factor (HGF).

The main feature of HGF-X7 is that it has been designed to efficiently express two isoforms of HGF simultaneously in the same way as in the human body by inserting a portion of the intron base sequence into a specific site of HGF cDNA. In addition, since there are no changes in the coding regions of HGF, the HGF proteins expressed by Engensis (VM202) are identical to the proteins produced in vivo.

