3.8 Results of Previously Conducted Clinical Studies

[figure not shown]

in the clinical study

[figure not shown]

[figure not shown]

Results of safety assessment: The tolerated dose of Engensis (VM202) administered in the ischemic myocardium of subjects with angina pectoris was 2 mg. A total of 112 cases of adverse events occurred in the nine subjects that participated in the clinical study, but there were no adverse events directly related to Engensis (VM202), and most were typical adverse events that were due to the worsening of underlying diseases or that occur after coronary artery bypass surgery. The quantity of HGF protein in blood was maintained at a stable level without any special changes during the follow-up period, and it was verified that antibodies for the HGF protein expressed by Engensis (VM202) were not produced.

Assessment of preliminary efficacy: The results of preliminary efficacy assessment using myocardial MIBI-SPECT, cardiac MRI, and echocardiography showed statistically significant improvement effects on the intramyocardial perfusion (before administration vs. at three or six months after administration, p < 0.05) of the Engensis (VM202) administration site, the myocardial thickness at end systolic phase and end diastolic phase of the left ventricle (before administration vs. at three months after administration, p < 0.05), and the myocardial wall motion index (before administration vs. at six months after administration, p < 0.05).

In the phase 1 clinical study on subjects with angina pectoris, it was verified that the tolerated dose of Engensis (VM202) was 2 mg, and adverse events that were directly related to Engensis (VM202) were not observed. These results show that the method of administering Engensis (VM202) into the ischemic myocardium is safe for patients with angina pectoris who undergo coronary artery bypass surgery, and that it improves the blood flow by inducing angiogenesis within the injected myocardium. In addition, the results also show the potential of the drug to fundamentally improve cardiac functions by recovering the thickness of ischemic myocardium through protective effects on the myocardium.

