#### 2. Establishment of Analysis Set

Efficacy assessment shall use the intention-to-treat (ITT) populations as the analysis sets, and analysis shall be performed on the auxiliary per-protocol (PP) sets. The definition of each analysis set for the assessment of safety, tolerability, and efficacy is as follows:

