#### (5) HGF antibody production by Engensis (VM202)

The presence or absence of HGF antibody (anti-HGF Ab) in blood was verified with the ELISA method. A preliminary assessment was performed on whether antibody production is correlated between the subject group determined to have increased muscle mass and improved function, and the subject group not determined as such.

However, if antibodies in blood were not produced in any of the subjects, the results were not presented.

The antibody test for hepatocyte growth factor was performed at Visit 2 (Day 0) and Visit 7 (termination visit, Day 270) (performed prior to administration at Visit 2 [Day 0]).

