#### (5) HGF antibody generation by VM202

: Descriptive statistics (frequency, percentage) shall be presented for the HGF antibody production at the termination visit (DAY 270) compared with the baseline (DAY 0). A contingency table shall be prepared for the differences at the termination visit compared with the baseline, and analysis shall be performed using the McNemar's test.

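### Anti-HGF antibody, the only immunogenicity measure, is analysed solely as an efficacy item: early-termination samples have no stated use, and the result is never set beside adverse events

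*SAP*

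**What the plan says.** The primary objective in SAP 1.1.1 is "To evaluate safety and tolerability following repeated doses of the investigational product (VM202"). The secondary objective in SAP 1.1.2 is "To evaluate efficacy following repeated doses of the investigational product (VM202"), and its fifth item is "5) HGF antibody generation by VM202". Protocol 5.1 and 6.2 file the antibody the same way. The safety endpoints (protocol 6.2, SAP 3.2) are adverse events, haematology, chemistry, urinalysis and vital signs. No antibody is among them, and the schedule contains no other immunogenicity assay.

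As an efficacy item the antibody falls under the rule in SAP 2: "Efficacy assessment shall use the intention-to-treat (ITT) populations as the analysis sets", with the per-protocol set as auxiliary. SAP 4.8(5) asks for frequencies, a contingency table and McNemar's test on "HGF antibody production at the termination visit (DAY 270) compared with the baseline (DAY 0"). SAP 3.3(5) adds one relation to an outcome: "A preliminary assessment was performed on whether antibody production is correlated between the subject group determined to have increased muscle mass and improved function" against the remaining subjects. SAP 3.3(5) and protocol 8.4.4(5) both say that no result is presented if no subject produced antibody.

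The schedule in protocol 6.1 marks the antibody test at early termination as well as on Days 0 and 270. Protocol 6.1.8 covers Visit 7 and early termination under one heading, though its antibody paragraph names only Visits 2 and 7.

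**The concern.** An antibody to HGF is not in itself a benefit, and the protocol does not treat it as one elsewhere. Under the safety results of the angina study, protocol 3.8 states that "it was verified that antibodies for the HGF protein expressed by Engensis (VM202) were not produced". Protocol 3.7 places the mouse humoral-response experiment under toxicity. Protocol 3.6 says that "the HGF proteins expressed by Engensis (VM202) are identical to the proteins produced in vivo", which makes it reasonable to ask whether an induced antibody could bind the subject's own HGF. That last step is an inference; no section names it as a risk.

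Three things follow from handling the antibody only as efficacy. A sample from a subject who stops early is drawn, but no rule brings it into the analysis. Antibody status appears in no adverse-event summary (SAP 4.7) and is not among the six subgroup factors (SAP 4.9). An all-negative finding, which is a safety result, would go unreported. In a 12-subject study whose primary question is the safety of repeated dosing, these gaps cost information already collected.

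**Working it through.** The plan gives no antibody rate, dropout rate or power figure, so there is no stated number to reproduce. The check traces the sample through the plan and then sizes the consequences at n = 12 (protocol 5.3.1, SAP 1.4.1).

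**1. Who is in the analysis set.** ITT (SAP 2.2.1) needs dosing and at least one efficacy assessment, whatever the visit compliance. Efficacy assessments are made before the first injection on Day 0 (protocol 6.1.2.1). Nearly every dosed subject therefore qualifies, and ITT probably equals the Safety set.

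**2. Which sample is used.** The schedule collects at Day 0, Day 270 and early termination. SAP 3.3(5) names Day 0 and Day 270, and SAP 4.8(5) analyses Day 270 against Day 0. SAP 4.3 does not impute values missing through early termination and uses the data available, without saying whether an early-termination sample counts as the post-dose value. This is where a sample can be lost.

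**3. Illustration of that loss (invented case).** Suppose 2 of 12 subjects stop early, both are positive at early termination, and no completer is positive. Exact Clopper-Pearson 95% limits, with zero-event upper limit 1 − 0.025^(1/n):

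- Day 270 only: 0/10, upper limit 1 − 0.025^(1/10) = 30.8%.
- With the early-termination samples: 2/12 = 16.7% (2.1% to 48.4%).

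**4. What the non-presentation rule hides.** For 0/12 the upper limit is 1 − 0.025^(1/12) = 26.5%. The chance that all 12 are negative is (1 − p)^12, for assumed true rates p:

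| Assumed p | P(at least 1 positive) | P(all negative) |
|---|---|---|
| 5% | 46% | 54% |
| 10% | 72% | 28% |
| 20% | 93% | 7% |

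An all-negative result is thus quite possible at a true rate of 5% or 10%, and its interval is worth printing.

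**5. Whether a test against adverse events would help.** With one positive subject among 12, the smallest possible Fisher p-value is 1/12 = 0.083. With two positives and perfect separation it is 1/66 = 0.015. The planned before-after comparison has the same limit: exact McNemar with d conversions all one way gives 2 × 0.5^d, so d = 5 gives 0.0625 and d = 6 gives 0.031. A listing carries nearly all the information.

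**6. Timing.** The last injection is nominally Day 104, so a Day 270 sample is taken 270 − 104 = 166 days later. Protocol 7.2.2 defines injection site reactions as occurring within 24 hours of injection. The sample cannot show antibody status at the time of such a reaction.

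**The case against.** Filing the antibody under efficacy is defensible. An antibody that binds HGF might blunt the product, so relating it to response is a fair question, and the planned frequencies keep positive results visible. Clinical immune events are already in the primary safety analysis: SAP 4.7 gives counts and Clopper-Pearson intervals for TEAEs, ADRs, AESIs and SAEs, injection site reactions are an AESI, and allergic reaction is a listed expected event. The human result cited is that no antibodies appeared, and the nonclinical work reports no immunostimulatory effect. All of this stands.

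It also stands that the early-termination gap rests on a literal reading. Protocol 6.1.8 joins the two visits under one heading, and available-data wording could be taken to include the sample. The SAP is ambiguous here rather than explicit in excluding it.

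A reader might infer that an efficacy-style completer analysis discards early stoppers. The documents do not support this: the main set is ITT, and only the auxiliary per-protocol set requires all visits. A reader might also infer that the antibody belongs among the primary safety endpoints of SAP 3.2. That would promote a secondary endpoint after enrolment closed (protocol 5.7.1), in an open-label study, and reporting it properly does not require it.

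**Conclusion.** The concern holds in a limited form. The only immunogenicity measure is handled solely as efficacy. SAP 4.8(5), read literally, leaves out a scheduled post-dose sample from anyone who stops early. No adverse-event display uses antibody status, and an all-negative result would not be shown. The protocol's own treatment of this measure as safety in the angina study argues for reporting it that way here.

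The size is modest. If every subject reaches Day 270, no sample is lost. The 0/10 against 2/12 contrast shows direction only and is not a forecast, because the documents give no dropout or antibody rate. The firm figure is the 26.5% upper limit for 0/12. The conclusion assumes that ITT and the Safety set coincide and that early-termination samples are drawn as scheduled. A reader might go further and conclude that immune-type harm goes unmonitored, or that an antibody-by-reaction table would show cause. Neither is supported: those clinical events are already captured and summarised, and the completers' antibody sample comes about 166 days after the last injection. This is a worthwhile low-cost improvement, not a threat to the primary analysis.

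**What to change.** Keep anti-HGF antibody as a secondary endpoint, and change the SAP as follows.

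- Report it as a safety/immunogenicity outcome in the Safety set, with count, percentage and Clopper-Pearson 95% interval, the method already used for adverse events.
- Define the post-dose value as the Day 270 sample or, if absent, the early-termination sample, flagged with its study day.
- Add a descriptive subject listing of antibody status beside TEAEs, ADRs and AESIs, with no formal test and a note that the Day 270 sample is taken long after the last injection.
- Report the result even when every subject is negative.
- Keep the comparison with muscle mass and function as exploratory.

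The cost is SAP wording and one listing, with no new sample, visit or subject. Protocol 8.4.4(5) carries the same Day 270 wording and non-presentation rule, so the SAP should record these points as departures from it. The drawback is that early-termination samples come at varying times after dosing and are not strictly comparable with Day 270, which is why each should be flagged with its day.

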#### 1.2 Clinical Study Design

The progression and procedures of this clinical study are as shown in the figure below.

Figure 1. Schematic diagram of clinical study

#### 1.3 Clinical Study Subjects

#### 1.3.1 Inclusion Criteria

Subjects enrolled in this clinical study must satisfy all of the following inclusion criteria:

- Males and females ≥ 19 years of age and ≤ 65 years of age
- Patients with confirmed diagnosis of CMT1A by genetic testing
- Patients with mild-to-moderate severity assessed by Charcot-Marie-Tooth Neuropathy Score version 2 (CMTNS-v2) with a score > 2 and ≤ 20
- 4) Individuals with lower limb muscle weakness with minimum dorsiflexion or more
- Individuals who voluntarily consented to participate in this study and signed the IRB-approved informed consent form after listening to a description on the characteristics of this clinical study prior to all screening tests
- 6) Individuals who can comply with the requirements in the clinical study
- In case of females of child-bearing potential, those who test negative in a urine or serum pregnancy test at screening
- 8) Individuals who practice medically approved contraceptive methods\* throughout the clinical study

#### \*Definitions

- · Drug: Oral contraceptives, skin patches, or progestin formulations (implants or injections)
- · Barrier method: Condoms, diaphragms, intrauterine devices (IUDs), vaginal suppositories
- Sexual abstinence: Complete abstinence (However, periodic abstinence (e.g., calendar method, ovulation method, and sympto-thermal method) and self-restraint are not considered as acceptable methods of contraception.)

#### 1.3.2 Exclusion Criteria

Subjects will be excluded from this clinical study if any one of the following criteria is met:

- Patients with significant respiratory, circulatory, renal, gastrointestinal, hepatic, endocrine, hematologic, psychiatric disorders or other severe diseases, or alcohol or drug addiction who may develop safety issues or cause confusion in the interpretation of the clinical study results as determined by the principal investigator
- 2) Patients with other neuromuscular diseases or neuropathy-inducing factors: Patients with chronic alcohol addiction, undergoing anticancer chemotherapy, or taking neurotoxic drugs
- Patients diagnosed with diabetes
- 4) Patients diagnosed with inflammatory bowel disease
- 5) Patients with a history of stroke or cerebral ischemic attack within 12 months prior to the screening date

- 6) Patients with a history of coronary artery disease, such as myocardial infarction and unstable angina pectoris, within 12 months prior to the screening date
- Morbidly obese patients with body mass index (BMI) ≥ 37
- 8) Patients who underwent orthopedic surgery (corrective surgery for bone and ligament, artificial joint implantation, osteosynthesis, osteotomy, arthroscopic surgery) in the lower limbs within 6 months prior to the screening date
- 9) Patients who may be affected by the muscle strength measurement test due to ankle contracture or surgery
- 10) Patients with uncontrolled hypertension (if systolic blood pressure is ≥ 160 mmHg or diastolic blood pressure is ≥ 100 mmHg at screening)
- 11) Within the last 5 years prior to the screening date, patients or patient's immediate family members (parents, siblings, offspring) with a history of malignant tumors, excluding basal cell carcinoma or squamous cell carcinoma that occurs on the skin (if it is determined that there is no possibility of relapse after resection), or with a family history of familial adenomatous polyposis (FAP) or hereditary nonpolyposis colorectal cancer (HNPCC)
- 12) Patients who have not completed a national cancer screening program applicable to their sex and age (date of birth) (if it cannot be confirmed that the relevant test was received at a national cancer screening center or a recognized screening center)

However, if it is confirmed that the relevant test was received at a national cancer screening center or a recognized screening center during the screening period, and that the results were within normal range, the patients may participate in the clinical study.

Common to males and females: If a patient is  $\geq 50$  years of age, the results of a colonoscopy within 5 years prior to the screening must be determined as being within normal range, and if adenomatous polyps are evident, the results of a colonoscopy within 1 year must be determined as being within normal range (inflammatory polyps or hyperplastic polyps are included in the normal range). If a patient is  $\geq 40$  years of age, the results of a gastroscopy within 2 years prior to the screening must be within normal range. If a patient is  $\geq 54$  years of age and has a 30 pack-year history of smoking or more, the results of a low-dose chest CT within 2 years prior to the screening must be within normal range. In case of liver cancer, carriers of hepatitis B or hepatitis C virus and patients with hepatic cirrhosis fall under the exclusion criteria. Females: For females  $\geq 40$  years of age, normal range findings must be confirmed in a mammogram within 2 years. For females  $\geq 20$  years of age, normal range findings must be confirmed in a Pap smear within 2 years.

- 13) Patients diagnosed with active pulmonary tuberculosis
- 14) Patients with HBV or HCV
- 15) Patients who test positive in human immunodeficiency virus (HIV) antibody test
- 16) Patients in an immunocompromised state due to treatments such as immunosuppressants, anticancer chemotherapy, and radiotherapy
- 17) Patients with a history of mental disease, which may interfere with study participation, within 6 months prior to the screening date
- 18) Patients who must take medications, that are known to have significant drug interactions within 14 days after the first administration of the investigational product or deemed unsuitable by the investigator's judgment
- 19) Individuals who participated in another clinical study\* within 6 months from the time of screening

### \*Definitions

- Drug: Those who participated in another clinical study within 6 months before the time of screening shall be excluded.
- Medical device: Those who participated in a noninvasive clinical study may participate in this clinical study if
  the principal investigator determines that the safety or pharmacodynamic assessment will not be
  affected.

- Individuals who have shown significant adverse events such as hypersensitivity reactions to the investigational product
- 21) Pregnant or breastfeeding females
- 22) Other individuals determined ineligible by the principal investigator to participate in the clinical study due to other reasons including clinical laboratory test results

#### 1.4 Number of Subjects

#### 1.4.1 Target Number of Subjects and Rationale for Calculation

Using this investigational product, clinical studies have been conducted on six diseases in total since 2007. Although there were no cases in which the drug was applied to CMT1A patients, a total of 18 subjects were recruited in a clinical study on amyotrophic lateral sclerosis among these studies. As a result of assessing safety, it was intended that this clinical study be conducted with 12 subjects considering the addition of indication and the slow progression of disease even though this clinical study also targets similar symptoms.

